8.1.3.1 Visit 2a for Patients on Prophylaxis Undergoing PK Evaluation

....

The samples taken 30 min post dose must not be taken from the same vein as previously used for administration of N8-GP. The lines/tubes must be flushed immediately after administration of the trial product.

~~Patients will be provided with an eDiary and will be carefully trained in the use of this eDiary including instruction in reporting details of bleeding episodes and prophylactic including doses administered at all visits after visit 2b.~~

The following will be performed and/or recorded in the eCRF:

Assessments to be made before the PK session at the day of dosing

- Confirmation of inclusion and exclusion criteria, see section 6.2 and 6.3
- Withdrawal criteria, see section 6.5
- Concomitant medication at all time points during PK, see section 11
- Check date and time of last coagulation factor administration (see section 8.4.3)
- AEs, see section 12.1
- Body measurements (weight only), see section 8.4.2
- Physical examination, see section 8.3.3
- Vital signs, see section 8.3.4
- ~~eDiary dispensing~~

.....

Laboratory assessments are to be analysed at central Laboratory

~~Training~~

- ~~• eDiary training, see 5.3 and 8.4.3~~

8.1.3.2 Visit 2b for Patients on Prophylaxis Undergoing PK Evaluation

The second dose of N8-GP will be administered at the site after the last PK sample is taken.

Patients will be provided with an eDiary and will be carefully trained in the use of this eDiary including instruction in reporting details of bleeding episodes and prophylactic treatment including doses administered at all visits after Visit 2b.

Four days after first dose the following assessments will be performed and/or recorded in the eCRF

- Withdrawal criteria, see section 6.5
- AEs: before and after dosing, see section 12.1
- *e-Diary training, see section 5.3 and 8.4.3*
- *e-Diary dispensing*
- ~~• eDiary data review and rate severity of bleeding episodes 8.2.1~~
- Home treatment/e-Diary training, see section 5.3 and 8.4.3
- Drug accountability for the trial medication dispensed or returned from the previous visits must be recorded in IV/WRS, see section 10.

.....

8.1.4 Visit 14-n and EOT Visit- visit in the Extension Phase of the trial

Before any trial related procedures/activities related to the Extension Phase of the trial, the patient and/or the LAR must have signed the informed consent form after having received written and verbal information about the Extension Phase part of the trial.

It should be decided if the patient is eligible to be part of the randomised group in part 1 of the Extension Phase before the patient comes for Visit 13 (EOM) and 14. If the patient for the last 6 months (180 days) prior to Visit 13/14 only has had 0 - 2 bleeding episode the patient is eligible for randomisation. If the patient is eligible to be in the randomised part of the Extension Phase part 1 and the patient has agreed to be part of the randomisation group, the patient should give written consent through the informed consent addendum so agreement to randomisation is documented. Recruitment into the sub-group of the Extension Phase part 1 will stop approximately at mid-May

2014, hereafter also patients with a low bleeding rate will continue the same treatment as in the Main Phase.

When patients randomised in part 1 have completed the part 1, all patients can start part 2 at their next visit beginning at visit 17. Skipping visit 15 and/or 16 should be entered with a comment in EDC.

While performing the EOM visit, IV/WRS will collect the response whether or not the subject will be randomised. For the subjects who are willing to be randomised, IV/WRS will then randomise the subject to either once weekly prophylaxis or every 4 day prophylaxis arm. For subjects who are not eligible or unwilling to be randomised, IV/WRS will dispense the trial product according to their chosen treatment regimen. The patient should be instructed to follow the treatment regimen in the assigned treatment arm. The numbers of bleeding episodes should be counted before all visits from visit 13 in preparation for a potential change in dosing regimen.

The home treatment period for patients on prophylaxis and on-demand is approximately 8 weeks (\pm 2 week) between visits during the first 4 visits in the Extension phase part 1 (Visit 14-17) and 12 weeks apart in part 2 (from the Visit 17), see Table 2-3.

Visit 14 will take place at the same day as Visit 13 in the Main Phase of the trial.

Antibody samples will only be drawn from patients in the on-demand arm at visits if they have received treatment during the home treatment period since last visit.

The samples taken post dose must not be taken from the same vein as previously used for administration of N8-GP.

The following will be performed and/or recorded in the eCRF at all visits during the Extension Phase:

- *Withdrawal criteria, see section 6.5 (not at Visit 14)*
- *PRO questionnaires, Visit 17, and every 4th visit approximately every year (Visit 21, 25...) and EOT, see section 8.4.5*
- *Concomitant medication, see section 11 (not at Visit 14)*
- *Check date and time of last coagulation factor administration, see section 8.4.3 (not at Visit 14)*
- *AEs: Since previous visit, see section 12.1 (not at Visit 14)*
- *Body measurements, see section 8.4.2 (not at Visit 14)*
- *Physical examination at Visit 17 and every 2nd visit (Visit 19, 21...) and at EOT, see section 8.3.3*
- *Vital signs, (before dosing if dosing take place at visit, not at Visit 14), see section 8.3.4*
- *ECG at Visit 17 and every 4th visit (Visit 21, 25...) and at EOT, see section 8.3.5*
- *e-Diary data review and rate severity of bleeding episodes, see section 8.2.1 (not at Visit 14)*

- *Home treatment/e-Diary training (not at EOT) if applicable*
- *N8-GP administration, not for on-demand patients (stop time of injection must be recorded in the eCRF, this corresponds to time “0”) (not at EOT)*
- *Dosing regimen choice or change and reason if change (not at visit EOT)*
- *Affirmation statement (at EOT Visit)*
- *End-of-trial form (at EOT Visit)*

On EOT form the first date on trial product refers to trial drug in this trial, and not trial drug taken as part of pathfinder™ 1, if the patient has participated in pathfinder™ 1.

Blood sampling for local laboratory assessments:

- *Haematology (to be taken within 1 hour prior to dosing), see section 8.3.6.1 (not at Visit 14)*

Blood sampling for central laboratory assessments:

- *Biochemistry, see section 8.3.7.1 (not at Visit 14)*
- *FVIII activity (trough level and recovery), i.e. before dosing (not at Visit 14) and 30 min (± 5 min) after dosing. Recovery not to be done in the on-demand arm and at EOT Visit, see section 8.3.7.3*
- *FVIII inhibitors, see section 8.3.2.2 (not at Visit 14)*
- *N8-GP binding antibodies, see section 8.3.2.1 (not at Visit 14)*

IV/WRS:

- *Drug accountability for the trial medication dispensed or returned from the previous visits must be recorded in IV/WRS (not at Visit 14), see section 10*
- *Dispensing of N8-GP for clinic dosing/home treatment must be performed via IV/WRS (for Visit 14 done together with Visit 13 (EOM) call, not at EOT) , see section 10*
- *Completion session in IV/WRS (at EOT Visit)*

Reminders for each visit:

- *An appointment for the next visit should be made (not at EOT Visit).*
- *Withhold N8-GP minimum 96 hours prior to next visit (not at EOT Visit)*
-

Telephone Contact:

It is recommended that a phone call is made to patients who have changed prophylaxis treatment regimen approximately 4 weeks or at time which seem appropriate after the change.

No same assessments should be done both at Visit 13 (EOM) and Visit 14. Data may be transferred from Visit 13 and to Visit 14 and vice versa.

....

8.1.7 Transfer of Patients to pathfinder™ 3 due to Major Surgeries

In case major surgery is needed the patients should be transferred to the pathfinder™ 3 trial. To enable patients to be transferred the following assessments have to be performed:

- To ensure that N8-GP is available for the surgery, notify the IV/WRS system at least 14 days prior to a planned surgery by using the IVRS "Dispensing session". This ~~can~~ *should* be done ~~both at a planned and unscheduled~~ visits.
- At the day of transferring to the pathfinder™ 3 trial the IV/WRS "Major surgery transfer" session should be used in order to transfer the patient into pathfinder™ 3
- Drug accountability – the patient must return and account for all drug dispensed in the current trial before entering pathfinder™ 3
- After completion of pathfinder™ 3 trial an IV/WRS "surgery transfer session" should be performed in order to transfer the patient into pathfinder™ 2
- ~~Fill in the Surgery transfer form in the eCRF~~

Upon completion of pathfinder™ 3, patients may return to pathfinder™ 2, re-entering the prophylactic or on-demand treatment arm as per their prior participation in the trial. The patient will return to the next visit in line in pathfinder™ 2 and the visit assessments performed at the EOT visit in pathfinder™ 3, will be used. The patient enrolled in pathfinder™ 2 with the intention of entering the pathfinder™ 3 for major surgery at the end of normal recruitment period in pathfinder™ 2 will not have to complete Visit 7 and reach 50 EDs before continuing into the Extension ~~trial~~ Phase of the trial if the Extension ~~trial~~ Phase is open. Though, a Visit 13 (EOM) must take place before continuing into the Extension ~~trial~~ Phase. Furthermore, the opening of the Extension ~~trial~~ Phase will not await these patients to complete 50 EDs in the Main Phase of the trial.

In case patients who had surgery in pathfinder™ 3 cannot follow the normal visits in the flowcharts (see figure 8-1 and 8-2) the patient can start at Visit 3, if the trial is in the period of the Main Phase, or Visit 14 if the trial is in the Extension Phase. The surgery patients do not have to complete all visits in the Main Phase before continuing into the Extension Phase, but need to follow the visit frequencies and need to have the Visit 13 (EOM) before continuing into the Extension Phase. If patients cannot return to the treatment regimen as before surgery, the investigator must choose the most appropriate regimen within the possibilities of the current phase of the trial.

8.2 Efficacy Assessments

8.2.1 Bleeding Episodes

During the entire trial period all treatment requiring bleeding episodes (*after Visit 2b*) will be entered by the patient or caregiver in the patient's eDiary. In case a patient is unable to enter a bleeding episode in the eDiary or hospitalised the Investigator will have to report it in the eCRF as an unscheduled visit, please refer to section 8.1.6.

...

8.3.2 Antibody Assessments

Blood samples for assessment of antibody formation against N8-GP will be drawn at the screening visit, pre-dose of N8-GP administration at all visits (except Visit 2b, *Visit 14*). *Antibody formation is also assessed in case of* at the follow-up visit approximately one month after the End of Trial visit. Antibody samples will only be drawn from patients in the on-demand arm at Visit 3-13 if they have received treatment during the home treatment period since last visit. The samples will be analysed both using the Bethesda assay identifying inhibitory antibodies towards FVIII and using an assay capable of identifying the occurrence of any antibodies towards ~~both FVIII and~~ N8-GP.

8.3.2.1 N8-GP antibody assay

...

Levels of N8-GP binding antibodies will be compared by *Novo Nordisk* to pre-dose samples throughout the trial. If a patient develops N8-GP binding antibodies and the incremental recovery value at that visit is less than 60% of screening value *and FVIII level at time of inhibitor sampling (pre-dose) is more than 0.015U/mL*, *Novo Nordisk will ask the Investigator to call the patient for an unscheduled visit for collection of a new inhibitor sample which should* will be taken after a 7 days wash out period.

A patient that tests negative for inhibitors following a 7 days wash out will confirm a negative inhibitor test and the patient will continue in the trial.

This algorithm will not apply for those who enter the trial with positive *test for* N8-GP binding antibodies and will not be triggered more than twice for an individual patient, *unless increases in antibody levels are observed*. Furthermore, a 7 days wash out period will only be applied if the 96 hours wash out is not sufficient to avoid drug interference in the inhibitor assay.

N8-GP antibodies results will be reported to site at EOM and EOT.

....

8.3.2.3 Antibody Assessments in case of Allergic/Anaphylactic Reaction

Any patient who experiences an ~~unexpected~~ *acute severe* allergic/anaphylactic reaction will be assessed for inhibitors and antibodies against drug product content, such as IgG/IgE against N8-GP and Host Cell Proteins (HCP). Additional blood samples may be requested for this purpose. If it is deemed necessary, the same analyses will be performed for all patients enrolled in the trial using available blood samples.

....

8.3.5 ECG

ECG must be performed at Screening (Visit 1), *End of Main Phase, at Visit 17(end of part 1), every year during Extension Phase part 2 (Visit 21, 25...)* and EOT visit. ECGs will be performed using a 12-lead Electro Cardiogram. For the ECG recording the patients must be resting and in a horizontal position. Any irregularities observed during the ECG e.g. cough, should either induce a re-run of the ECG and/or be annotated in the eCRF page with description of the occurrence. Print-outs must include date, time, patient's identification, and initials of the Investigator, and at least 2 complexes for each lead and a single rhythm strip of 6 beats. Electronic capture of these measurements may also be performed.

....

8.3.7.3 FVIII Activity (central laboratory)

...

Exploratory assays for measuring N8-GP activity

A non validated exploratory Thrombin generation assay (TGA) and/or other assays can be applied for measuring activity of N8-GP and analysed by the end of *main phase and by end of* the trial. The results from these assays will be reported separately.

...

8.4.2 Body Measurements

All body measurements (weight, height and BMI) will be performed at Visit 1. *During the Extension Phase patients under 18 years will have their height measured yearly.* On all other visits only weight will be measured. The weight measured at the respective visits should be used for calculating the amount of N8-GP to be dispensed and the dose of N8-GP to be administered.

- Weight (registered with one decimal), wearing light clothing only (kg/pounds) and without shoes
- Height, without shoes (cm/inches), Visit 1 only
- BMI calculation (kg/m^2), Visit 1 only

...

8.4.4 Medical History/Concomitant Illness

....

Haemophilia Details (including history)

- Diagnosis of haemophilia A (date)
- Other coagulation related diseases
- Classification of haemophilia A (severe form requested in this trial – *only collected as confirmation of inclusion criterion 2*) and FVIII:C activity level (%) from medical history
- Underlying gene defect (if known)
- Clinical suspicion of inhibitors data from medical history
- Number of inhibitor tests and/or FVIII:C recovery tests within the last 8 years
- History of switching FVIII products (type of products (from/ to) and age at switching) if available
- Relatives with haemophilia A (yes/no)
If yes – specify any relatives with haemophilia A and inhibitors (as recalled by patient)

...

8.4.5 PRO Questionnaires and Health Economics

PROs will be collected at screening visit (Visit 1), *at Visit 17 (end of part 1) and every year during Extension Phase part 2 (Visit 21, 25...)* ~~and at EOT~~ *End of Trial* visit for all patients. The questionnaires should preferably be completed prior to any other trial related activities during the two visits. Health economic data will be collected after treatment starts in connection with bleeding episodes.

Several questionnaires will be used to assess disease and age-group specific quality of life and treatment satisfaction from the screening and *until* EOT Visits.

The following questionnaires should be completed by the patients and, where relevant, also by the parent/LAR:

For trial patients aged 12-16:

HAEMO-QOL: Questionnaire for children/adolescents (8-12 years, 13-16 years)

EQ-5D: Questionnaire (13 years and above)

HAEMO-QOL: Parents proxy; Questionnaire for parents/LARs of Children/adolescents (8-12 years, 13-16 years)

HEMO-SAT(P): Parents proxy; Questionnaire for parents/LARs of adolescents (13-16 years)

For trial patients aged 17 and above:

HAEM-A-QOL: Questionnaire for adults aged 17 and above

HEMO-SAT(A): Questionnaire for adults aged 17 and above

EQ-5D: Questionnaire (13 years and above)

The patient (and parents or LAR(s) if applicable) should throughout the trial complete the questionnaires corresponding to his age group at screening visit despite the patient changes age group during the trial.

....

8.5.1 Definition of Treatment Compliance

Good compliance: If the prophylaxis infusions of N8-GP is 50 U/kg BW \pm 5 U/kg BW for at least 80% of the prophylaxis infusions and the time interval between two prophylaxis infusions is *as prescribed* ~~4 days~~ for at least 80% of the time.

Less compliance: If the prophylaxis infusions of N8-GP is outside 50 U/kg BW \pm 5 U/kg BW for more than 20% of the prophylaxis infusions or the time interval ~~if there is more or less than 4 days~~ between two ~~dosis~~ *prophylaxis infusions is not as prescribed* for more than 20% of the time.

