8.4.2 Body Measurements

All body measurements (weight, height and BMI) will be performed at Visit 1. On all other visits only weight will be measured. The weight measured at the respective visits should be the weight used for calculation of the dose administered.

- Weight, wearing light clothing only (kg/pounds) and without shoes
- Height, without shoes (cm/inches), (visit 1 only)
- BMI calculation (kg/m^2) (visit 1 only)

8.4.3 eDiaries

eDiaries will be used in this trial. The patient should bring the eDiary to every visit to the site.

The following data will, as a minimum, be captured by the patient or the caregiver in the e-Diary:

- Treatment
 - FVIII product used
 - Prophylaxis or treatment of bleed
 - Dose level
 - Date and time of dose administration
- Bleeding episodes
 - Onset of bleed (date and time)
 - Haemostatic drug used for treatment (dose and time of administration)
 - Pain relieving medication
 - Cause of bleed (spontaneous, traumatic, minor surgery)
 - Location of bleed
 - Other therapy used (compression, ice or other)

- Evaluation of haemostatic response (excellent, good, moderate, none)
- Stop of bleed (date and time)
- Bleed related days away from work or school
- Bleed related days using mobility aids

The Investigator must carefully instruct the patient in how to evaluate a bleeding episode, the haemostatic response after treatment and how to complete the eDiary.

The entries made by the patient in the eDiary will be reviewed by the Investigator together with the patient and/or caregiver during every visit to ensure consistency/compliance. The information in the patient's eDiary is regarded as source data. In case information missing in the eDiary is available in the medical records, this information can be used.

It is the investigator responsibility to rate the severity of all reported bleeding episodes in the eCRF.

Trial product administration performed at the site should also be entered in the eDiary by the patient.

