8.5 Patient Compliance

Assessment of patient compliance with the protocol procedures for determination of the continuation of the trial will be done at the Investigator's discretion. The Investigator or his designee can at any time access the patient data from the eDiary in a web portal.

Failure of compliance with scheduled visits and trial product administration may result in withdrawal in accordance with the protocol withdrawal criteria.

Compliance with the N8-GP treatment should be addressed at each visit. In the prophylaxis treatment, doses should not be separated by more than 96 hours. If patients experience bleeding episodes due to exceeding the time between doses indicated above, the Investigator must retrain the patient/parent/caregiver. The training must be documented in the medical records.

If a patient deviates from the 96 hours dose intervals mentioned above, but the dose is administered on the correct day, this is not considered a protocol deviation.

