- *0-2 bleeding episodes within last 6 months on same regimen would allow a less frequent dosing interval to a lowest frequency of every 7 day. Change to a less frequent treatment regimen should be done while the patient is at a site visit*
- *If a patient on every 7 day treatment regimen over a 8 week period experiences two or more spontaneous bleeding episodes or one severe bleeding episode requiring hospitalisation, then the patient must be switched back to every 4 day treatment regimen* ~~3 or more bleeding episodes within last 6 months on same regimen allows to stay on regimen or change to a more frequent regimen to a highest frequency of every 4 day~~
- ~~Change of regimen can only take place after being on the same regimen for at least 6 months~~

Clinical judgement has to be applied in order to avoid increased risk to the subject's safety and must always overrule ~~guidelines~~ *the above described rules* when deemed necessary by the Investigator.

The dose for the Extension Phase part 1 and 2 will be:

50 U/kg BW of N8-GP for prophylaxis treatment every 4 day

~~60 U/Kg BW of N8-GP for prophylaxis treatment every 5 and 6 day~~

75 U/Kg of N8-GP for prophylaxis treatment every 7 day

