1.1 Trial information

This phase 3 trial is a multi-centre, multi-national, open-label, non-randomised trial evaluating safety, pharmacokinetics and clinical efficacy of NNC 0129-0000-1003 (hereafter referred to as N8-GP) when used for treatment of bleeding episodes and for long-term prophylaxis. The trial consists of a Main Phase followed by an Extension Phase part 1 and part 2. In the main phase, patients in the prophylaxis arm were receiving one single bolus dose of 50 U/kg body weight (BW) of N8-GP every 4 days (96 hours interval).

In the extension part 1, patients with a low bleeding rate on every 4 day prophylaxis in the main phase have the possibility of being randomised to either 50 U/kg BW every 4th day or to 75 U/kg BW once weekly dosing. If the patient for the last 6 months (180 days) prior to Visit 13/14 only had 0 - 2 bleeding episodes, the patient was eligible for randomisation. Patients who were not eligible to be in the randomised arm or patients who are eligible but unwilling to be randomised can stay on the same regimen as in the Main phase.

In the extension phase part 2, patients with a low bleeding rate (0-2 bleeding episodes during the last 6 months) on every 4 day prophylaxis have the possibility of changing to 75 U/kg BW once weekly dosing regimen. Patients who has been on 75 U/kg BW once weekly dosing during extension phase part 1 can continue on this regimen arm or change back to either 50 U/kg BW every 4th day if the patients want to. Patients on once weekly dosing who have more than 2 spontaneous bleeds within a 8 week period or are hospitalised due to a bleed need to change back to every 4 days regimen according to the protocol.

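### The compliance dose band was left at 50 ± 5 U/kg when weekly dosing at 75 U/kg was added, so correct weekly dosing is rated as poor compliance

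*Protocol*

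**What the plan says.** Version 1.0 of the protocol had one planned prophylaxis dose, 50 U/kg, normally every 4 days, and section 8.5.1 defined compliance to match: 50 ± 5 U/kg for at least 80% of infusions, with a 4-day interval for at least 80% of the time.

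Amendment 13 (section 5.3.1) introduced a weekly regimen in the Extension Phase: "75 U/Kg of N8-GP for prophylaxis treatment every 7 day". Amendment 14 kept it, and SAP 1.1 confirms that eligible patients could be "randomised to either 50 U/kg BW every 4th day or to 75 U/kg BW once weekly dosing".

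Amendment 13 also revised 8.5.1, which now reads as follows:

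- *Good*: "Good compliance: If the prophylaxis infusions of N8-GP is 50 U/kg BW" ± 5 U/kg "for at least 80% of the prophylaxis infusions and the time interval between two prophylaxis infusions is" as prescribed for at least 80% of the time.
- *Less*: "Less compliance: If the prophylaxis infusions of N8-GP is outside 50 U/kg BW" ± 5 U/kg for more than 20% of infusions, or the interval between two "prophylaxis infusions is not as prescribed" for more than 20% of the time.

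The only change of substance is the interval, from 4 days to whatever was prescribed. The dose band is the same in both definitions. Section 8.5 retains its general sentence from version 1.0: "In the prophylaxis treatment, doses should not be separated by more than 96 hours". It goes on to require documented retraining when a patient bleeds because that interval was exceeded.

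**The concern.** The interval edit has no purpose other than to make 8.5.1 cover regimens other than every 4 days, yet the dose half of the same rule was not adapted. On the weekly regimen the dose rating is therefore inverted: the correct dose fails and a substantial under-dose passes. Because *Less compliance* is triggered by dose or interval, perfect timing cannot rescue a correctly dosed weekly patient.

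What is at stake is any compliance summary for the weekly regimen, whose safety and efficacy are the main objective of Extension Phase part 1, and the guidance given to investigators, who are told to address compliance at each visit. The 96-hour sentence adds to this. Read literally, a patient on weekly dosing who follows the protocol and bleeds on days 5 to 7 would fall under the retraining instruction.

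**Working it through.** **Inputs.** Dose band 50 ± 5 U/kg, with 80% of infusions required in band (Amendment 13, 8.5.1). Weekly dose 75 U/kg (5.3.1 as amended; SAP 1.1). Extension part 1 lasts 24 weeks (8.1 as amended; SAP 2.2.2). Main Phase treatment runs from 200 days to about 19 months, with a maximum of 27 months (5.1 as amended) and an expected average of about 12 months (18.1).

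**Weekly period on its own.**

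- Band: 50 − 5 = 45 to 50 + 5 = 55 U/kg.
- Every-4-day dose: 50 lies in the band, so the rule works as intended for that regimen.
- Weekly dose: 75 − 55 = 20 U/kg above the upper edge. Correctly dosed infusions in band: 0%, against the 80% required.
- Doses that do pass: (75 − 55)/75 = 26.7% to (75 − 45)/75 = 40.0% below the prescribed dose.

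**If earlier infusions are pooled in.** Section 8.5.1 names no evaluation period, so the alternative reading is to pool the Main Phase with part 1. Assume perfect dosing, every-4-day infusions n4 = floor(days/4), and 24 weekly infusions in part 1. The out-of-band share is 24/(24 + n4).

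| Main Phase duration | Days | n4 | Share out of band |
|---|---|---|---|
| Shortest | 200 | 50 | 24/74 = 32.4% |
| 12 months | 365 | 91 | 24/115 = 20.9% |
| 19 months | 578 | 144 | 24/168 = 14.3% |
| 27 months | 821 | 205 | 24/229 = 10.5% |

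The 20% limit is exceeded at the end of part 1 when 24/(24 + n4) > 0.20, that is when n4 < 4 × 24 = 96 infusions (384 days, about 12.6 months). A patient who stays on weekly dosing in part 2 exceeds it after floor(n4/4) + 1 weekly infusions: 37 after a 19-month Main Phase and 52 after 27 months. Among perfectly adherent patients, the label under pooling therefore depends on time spent on each regimen, not on adherence.

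**Interval sentence in 8.5.** 7 × 24 = 168 hours, against a stated limit of 96.

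**Later correction.** None of the later amendments provided revises 8.5 or 8.5.1, and the SAP contains no compliance definition that would override them.

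**The case against.** The strongest reply is that nothing reported depends on this. The Full Analysis Set and the Safety Analysis Set include every patient exposed to N8-GP, there is no per-protocol set, and the SAP does not use the *Good*/*Less* categories. The part 1 bleeding-rate analysis is by randomised regimen, with switchers from weekly dosing treated as withdrawals. All of that stands, and it caps the severity.

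The risk to actual dosing is also small. The weekly dose is stated plainly in 5.3.1, the IV/WRS dispenses by regimen, and eDiary entries are reviewed at visits. Withdrawal for non-compliance is at the investigator's discretion and is not tied to 8.5.1. Nothing in the documents suggests that anyone would give 50 U/kg weekly because of this rule.

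On the 96-hour sentence, one can say that the later, specific text in 5.3.1 governs the older general sentence, and that 8.5 does not count a departure from 96 hours as a deviation if the dose is given on the correct day. That softens the conflict but does not remove it, since the sentence and the retraining instruction attached to it remain in force.

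Finally, the pooled figures rest on an assumed evaluation period, and under pooling some correctly dosed patients escape the *Less* label. That is true, but the escape depends on a long Main Phase, so pooling does not make the rule valid.

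**Conclusion.** The concern holds, as a minor point. Applied as written to a weekly period, 8.5.1 misclassifies every patient dosed exactly as prescribed (0% of infusions in band) and accepts doses 27–40% too low on the dose criterion. The consequence is confined to compliance classification and reporting for the weekly regimen and to guidance for investigators; the planned efficacy, inhibitor and other analyses do not change.

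The conclusion rests on version 1.0 plus the amendments provided. The consolidated later protocol versions are not among the documents, although the amended text of 8.5.1 itself is shown directly. The pooled percentages additionally assume perfect dosing and pooling across the Main Phase and part 1. No view is taken on which dose or interval is clinically right.

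**What to change.** - **8.5.1:** define the dose window relative to the assigned regimen. For example, prescribed dose ± 10% keeps 45–55 U/kg for every-4-day dosing and gives 67.5–82.5 U/kg for weekly dosing. An absolute ± 5 U/kg (70–80 U/kg weekly) would serve equally well, provided one rule is chosen and stated.
- **8.5.1:** state that compliance is evaluated separately for each period on a regimen.
- **8.5:** replace the 96-hour limit with the prescribed interval, so that the retraining instruction also follows the regimen.

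The cost is wording in two sections. No new data are needed, because the eDiary (8.4.3) already captures the dose level and "Date and time of dose administration". The SAP is dated 14 January 2019, after the planned last visit of 3 December 2018, so the practical step now is a documented regimen-specific derivation, to be used if compliance is reported.
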